In a controlled setting, up to 30 participants, aged 21-39, will attend a session where they receive 3 doses of a standard amount of alcohol, based on weight and gender(Watson, Watson, & Batt, 1981), designed to raise Blood Alcohol Content to 1.02g/dL. Participants will receive their first dose of alcohol. After 30 minutes, breath alcohol content (BrAC) will be measured with the BacTrack Pro (BACtrack Mobile Pro, n.d.). To continue assessing the validity of the BacTrack Skyn device, some participants will be instructed to wear the Bactrack skyn at the beginning of the study.

For participants in the control group, they will remain blinded to their BrAC reading and complete the Self-Report of Intoxication Survey. For participants in the intervention group, they will be shown their BrAC reading on the BacTrack mobile app and then instructed to complete the Self-Report of Intoxication Survey.

A second dose and third dose will be given and this process will be repeated at 40 minutes and 80 minutes after the first dose. A study smartphone will be used to collect smartphone-paired breathalyzer readings. We will also measure self-reported intoxication rating using measures subjective intoxication: Personal Drinking Habits Questionnaire (PDHQ)(Vogel-Sprott, 1992), Perceived Driver Fitness(Van Dyke & Fillmore, 2014)and Perceived intoxication and BAC estimation(Harrison & Fillmore, 2005; Harrison, Marczinski, & Fillmore, 2007) administered by the study staff.

All research activities will be conducted in the CTRC and alcohol will be provided from Investigational Drug Service. All research staff will be fully trained in the pilot protocol and their role in the study, will be supervised by the PI, [name] [name], MD (Assistant Professor of Emergency Medicine), and will be trained to refer patients to the appropriate provider (emergency department, outpatient doctor/clinic, social worker) as warranted. A nurse, trained in the protocol, will be onsite at all times and able to assist if any adverse effects occur.

Study duration. List projected overall duration of the study including: 1. Estimated length of time to enroll all subjects and complete the study; 2. Length of a subject's participation time in study; 3. Project date of the proposed study.

Recruitment will take place for one month before the first study date, in order to enroll up to 30 participants in the study. Each subject will participate in one 5-6 hour study session. There will one to

two study sessions per week. The estimated duration of the study is 10 weeks. The projected start date of the proposed study is April 1, 2017.

#### Resources necessary for human protection

All research activities will be conducted in the CTRC and alcohol will be provided from Investigational Drug Service. The project manager will oversee all study operations and two research assistants will be trained in the protocol and present at the study sessions. All research staff will be fully trained in the pilot protocol and their role in the study, will be supervised by the PI, [name] [name], MD (Assistant Professor of Emergency Medicine), and will be trained to refer patients to the appropriate provider (emergency department, outpatient doctor/clinic, social worker) as warranted. A nurse, trained in the protocol, will be onsite at all times and able to assist if any adverse effects occur.

Target population. State the clinical condition, disease state, or population characteristics of primary interest, eg: "Adult subjects with a diagnosis of Type II diabetes for greater than two years."

Up to 30 men and women, ages 21-39, will be enrolled who self-report as moderate drinkers, who are not seeking treatment for alcohol abuse (i.e. no treatment in the past year and current verbal report of not wanting treatment) do not have alcohol use disorder, as defined by the DSM-V, and do not have any medical conditions that limit or prevent alcohol consumption. Because there are well known risks of alcohol to the unborn fetus, women will be screened with a urine pregnancy test and must confirm a negative result before alcohol is administered. Children will not be recruited for this protocol because alcohol will be administered and the legal drinking age is 21 years. Due to the risks involved with drinking and driving, participants will only be enrolled in the study if they are willing to take public transportation or a rideshare home from the study visit.

Subjects will be healthy volunteers, 21-39 years old. They will be non-treatment seeking community drinkers. Subjects will be included if they drink socially and have reported consuming (4 or more drinks for women, 5 or more drinks for men) during one occasion without problems. However, they will be excluded if they drink 4 or more days per week on average or consume on average 12 or more drinks per week. They will be excluded if they have met criteria for DSM-V (American Psychiatric Association 2013) alcohol use disorder (lifetime) or substance use disorder (within the past 12 months), or a psychiatric disorder that required hospitalization, are using psychotropic medications or are pregnant or nursing. Subjects will undergo a brief medical screening, female subjects will confirm that they are not pregnant using a urine screening.

#### Accrual

We plan to enroll up to 30 adults aged 21-39 who are moderate drinkers without dependence to complete this standardized drinking protocol. This is a pilot study aimed at collecting data to understand perceived fitness to drive a vehicle among intoxicated aimed to inform future research. It is expected that the majority of subjects will volunteer to participate after responding to IRB-approved advertisements on mass transit and broadcast email messages at institutions (including the University of Pennsylvania Health System) that offer such a service; and by posting/distributing recruitment materials

in community settings with public posting areas or other means of providing community access to materials (such as hospitals, town halls, public libraries, YMCAs, health fairs/organizations).

#### Key Inclusion Criteria

Inclusion criteria will be: (a) age 21-39 old, (b) Less than 4 drinking days and less than 12 drinks per week on average in the past 2 months, (c) have previously consumed four (women) or five (men) or more standard drinks without problems (d) a valid photo ID (e) willing to take public transportation home, via septa or a rideshare credit.

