the study. Explain if the research involves the review of records (including public databases or registries) with identifiable private information. If so, describe the type of information gathered from the records and if identifiers will be collected and retained with the data after it is retrieved. Describe the kinds of identifiers to be obtained, (i.e. names, social security numbers) and how long the identifiers will be retained and justification for use and/or evaluations.

We are planning to recruit and enroll up to 30 participants through recruitment material that will be sent out through email and posted on fliers (see recruitment material attached). Inclusion criteria will be: (a) age 21-39 years old, (b) less than 4 drinking days and less than 12 drinks per week on average in the past 2 months, (c) have consumed at least 4(women) or 5 (men) drinks on one occasion, in the past year without experiencing adverse effects (c) a valid photo ID (d) willing and able to use a rideshare credit or septa token as transportation home from the study visit. Exclusion criteria will be (a) desire alcohol treatment now or received it in the past 6 months, (b) alcohol use disorder with withdrawal per DSM-V criteria and (c) non-English-speaking, and (d) women who are pregnant (e) individuals who should not consume alcohol due to a medical condition. Individuals, who are interested in the study, will be contacted and screened over the telephone using our Alcohol Study Screener (attached to this protocol). All participants who meet inclusion criteria will be invited to consent to the study.

Interested participants will call the study hotline where an IRB-approved research assistant or project manager, will answer any questions, administer the study screening and go over the written informed consent. There will be an optional in person study visit for the participant to come in and review study procedures, and sign written informed consent, in person. At the study visit, which occurs at a predetermined time, the participant will first sign written informed consent to participate. They will then take an initial survey, with questions related to their past alcohol use and habits including Driving History and Experience Questionnaire DHEQ1, Drinking and Driving Questionnaire. Participants will also take the Decision making survey, which includes The Barratt Impulsiveness Scale, and the Delayed discounting questionnaire.

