1. Recruitment: We will use broad-based and cost-effective recruitment strategies including: a) advertisements in UPHS and CHOP employee weekly emails; and b) posting of flyers. Individuals, who are interested in the study, will be contacted and screened over the telephone.
2. Phone Screening: General information will be provided to the prospective subject. Study screening form (attached) will be administered, eligibility confirmed, and research staff will go over informed consent with participant. Participants will have the option to have the informed consent form emailed to them prior to the study visit. Columbia suicide severity rating scale will be administered. Inclusion criteria will be: (a) age 21-39 old, (b) Less than 4 drinking days and 12 drinks per week on average in the past 2 months, (c) have consumed either 4 (women) or 5 (men) or more standard drinks on a single occasion without problems (d) a valid photo ID (e) willing to take public transportation home, via septa or a rideshare credit. Exclusion criteria will be (a) desire alcohol treatment now or received it in the past 6 months, (b) alcohol dependence with withdrawal per DSM-V criteria (c) non-English-speaking, and (d) individuals who have a medical condition or who are taking medication which limits or prevents the consumption of alcohol. Interested and eligible participants will schedule their study visit.

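### Two inclusion lists admit to the alcohol challenge a person who has not drunk for years, whom three other eligibility statements exclude

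*Combined protocol and SAP*

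**What the plan says.** The protocol states the drinking conditions for entry in five places.

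- **Administration of Surveys and/or Process** requires that candidates "have consumed at least 4(women) or 5 (men) drinks on one occasion, in the past year without experiencing adverse effects". It limits recent drinking to "less than 4 drinking days and less than 12 drinks per week on average in the past 2 months".
- **Target population, first paragraph**, enrols people who describe themselves as moderate drinkers. The same sentence rules out treatment-seeking, alcohol use disorder and limiting medical conditions.
- **Target population, second paragraph**, begins "Subjects will be included if they drink socially and have reported consuming" and goes on to the four- or five-drink threshold on one occasion, with no period attached. It excludes people who drink above a weekly limit.
- **Key Inclusion Criteria** requires that candidates "have previously consumed four (women) or five (men) or more standard drinks without problems", and sets "Less than 4 drinking days and less than 12 drinks per week on average in the past 2 months".
- **Procedures, Phone Screening**, requires that candidates "have consumed either 4 (women) or 5 (men) or more standard drinks on a single occasion without problems", and sets "Less than 4 drinking days and 12 drinks per week on average in the past 2 months".

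Eligibility is applied by telephone. Candidates are "screened over the telephone using our Alcohol Study Screener (attached to this protocol"), and the Phone Screening step is where eligibility is confirmed. The screener is not among the documents available here.

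**The concern.** The trial gives three doses of vodka intended to reach a BAC of 0.10. Potential Study Risks puts this at 4 to 5 standard drinks and supports it by noting that these moderate drinkers have taken that much before. The prior-drinking item is thus the entry criterion on which part of the safety argument rests.

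If that item has a window in one place and none in others, and the companion item on recent drinking sets only a maximum, the answer for a long-term non-drinker depends on which section staff apply. At stake is whether someone whom the protocol excludes in one section can be enrolled and dosed under another.

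**Working it through.** The plan gives no figure to reproduce and no formula applies. The check sets the five statements side by side and applies each to one test case: a healthy adult aged 21 to 39 with no alcohol use disorder, one problem-free occasion of at least four (woman) or five (man) drinks some years ago, and no alcohol since.

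| Statement | One occasion? | Window on the 4/5-drink item | Limit on recent drinking | Current-drinking condition | Test case |
|---|---|---|---|---|---|
| Administration of Surveys and/or Process | Yes | Past year | Maximum only | None | Excluded by the window |
| Target population, 1st paragraph | No such item | No such item | None | Self-described moderate drinker | Excluded |
| Target population, 2nd paragraph | Yes | None | Maximum only | Social drinker, no time frame | Excluded |
| Key Inclusion Criteria | Not stated | None | Maximum only | None | Admitted |
| Phone Screening | Yes | None | Maximum only | None | Admitted |

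**Step 1, the window.** Four statements carry the 4/5-drink item. One of the four gives a window.

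**Step 2, the recent-drinking item.** In all three lists it is a ceiling. The test case has 0 drinking days and 0 drinks per week; 0 < 4 and 0 < 12, so the item is met. None of the three lists contains a minimum or a current-drinking condition.

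**Step 3, the exclusions.** Key Exclusion Criteria and the Phone Screening exclusions between them cover treatment wanted now or received in the past 6 months, alcohol or substance use disorder, psychiatric hospitalisation, non-English speakers, medical conditions or medication that restrict drinking, and suicidal ideation. None applies to a healthy person who simply stopped drinking.

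**Step 4, the count.** Three of the five statements exclude the test case and two admit it. The two that admit are Key Inclusion Criteria and the list used at telephone screening.

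**Step 5, a second disagreement with the same cause.** Take a current social drinker within the weekly limits whose last 4/5-drink occasion was more than a year ago. Of the four statements carrying the 4/5-drink item, three admit this person and only Administration of Surveys and/or Process excludes them.

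**The case against.** The strongest reply is that the protocol should be read as a whole. Target population and Accrual describe moderate drinkers, Target population makes social drinking a condition of inclusion, and nothing says that Key Inclusion Criteria overrides them. This stands in part. A reader might infer that the plan means to admit non-drinkers, and the documents do not support that; the defect is uneven restatement. It still matters, because the Phone Screening list, where eligibility is confirmed, is one of the two that lack the condition.

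Second, the screener and the eligibility survey may ask about recency. The optional eligibility meeting, the medical history and the intake survey on drinking habits could also reveal a long-term non-drinker. This stands: only an inconsistency of text is shown. The intake survey is not, however, described as an eligibility check.

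Third, a reader might infer that the safety rationale collapses. It does not. Potential Study Risks relies on previous intake of that amount and gives no period, and the Phone Screening item secures this. What fails for the test case is the description of subjects as moderate drinkers.

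Fourth, a reader might go further and say that the lists are wrong to admit someone whose last drink was 3 to 12 months ago, with a 4/5-drink occasion in that time. All three lists agree on that person, who meets the strictest prior-drinking item in the protocol, and nothing in the documents shows that such a gap makes the challenge unsuitable. That is a design preference and not an error.

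Finally, nothing marks the Administration of Surveys and/or Process list as governing. That is true, so adopting its window is a choice for the sponsor. Adding only the social-drinker condition would remove the main contradiction but leave the disagreement in step 5.

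**Conclusion.** The contradiction is real and lies in the current text. A healthy person who has not drunk for years meets every drinking item in Key Inclusion Criteria and Phone Screening, and is excluded by three other statements.

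The consequence is low to moderate. BrAC is measured after each of the three doses, there is a brief medical screening, and a nurse is onsite throughout. On the other side, neither Dose Administration nor the Timeline gives a reading at which the next dose is withheld. How many candidates would be affected is unknown; the trial enrols up to 30. No stated sample size or power figure changes.

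The conclusion assumes that the moderate-drinker wording in Target population works as a condition of entry, as its neighbours in the same sentence do, and that social drinking there means present drinking. If the moderate-drinker wording were only descriptive, two statements would still exclude the person and the contradiction would remain. If the attached screener already asks about the past year and about current drinking, the practical gap is closed and only the text needs correcting.

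**What to change.** Three edits, all using wording that the protocol already contains:

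1. In Key Inclusion Criteria and Phone Screening, and in the second paragraph of Target population for consistency, replace the 4/5-drink item with the version under Administration of Surveys and/or Process: "have consumed at least 4(women) or 5 (men) drinks on one occasion, in the past year without experiencing adverse effects". This also restores the single occasion missing from Key Inclusion Criteria.
2. Add the existing Target population condition (currently drinks socially, or describes themselves as a moderate drinker) to the three lists: Administration of Surveys and/or Process, Key Inclusion Criteria and Phone Screening. No new numeric minimum is needed.
3. Check that the attached screener asks both questions, and amend it if not.

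The cost is rewording one item in three places, adding one condition to three lists, and one check of a form. The downside is a few extra screen failures, including current social drinkers whose last 4/5-drink occasion was over a year ago. If the sponsor wants to keep those people, it should drop the window everywhere and rely on the social-drinker condition, so that all statements still agree.

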#### Key Exclusion Criteria

Exclusion criteria will be: (a) a desire for alcohol treatment now or received it in the past 6 months, (b) alcohol use disorder per DSM-V criteria and (c) substance use disorder within the past 12 months per DSM-V criteria (d) a prior psychiatric condition requiring hospitalization (e) non-English-speaking (f) individuals who have a medical condition or who are taking medication which limits or prevents the consumption of alcohol (g) suicidal ideation. We are excluding non-English speaking individuals due to the fact that we do not have translated materials so they will be unable to consent to participate in the study activities. We are also excluding individuals who are under 21 years in age due to legal restrictions of consuming alcohol. We are excluding individuals who have psychological or medical conditions, or are taking medication, that limit or prevent the consumption of alcohol.

#### Vulnerable Populations: Specify if the study intentionally includes any of the following populations:

#### Populations vulnerable to undue influence

This study may enroll employees or students of Penn. These participants will not be recruited directly or incentivized differently than other subjects in the study. During informed consent study staff will review the voluntary nature of their participation and reminded that they are able to leave the study at any time during the study procedures.

#### Subject recruitment: Overview the approach to subject identification and recruitment, including referrals from physician offices, clinics...

Subjects for this study will be recruited primarily from individuals who present themselves for evaluation for study inclusion by calling our research facility. It is expected that the majority of subjects will volunteer to participate after responding to IRB-approved advertisements on mass transit; and broadcast email messages at institutions (including the University of Pennsylvania Health System) that offer such a service; and by posting/distributing recruitment materials in community settings with public posting areas or other means of providing community access to materials (such as hospitals, town halls, public libraries, YMCAs, health fairs/organizations). We will obtain permission before distributing or posting the approved recruitment materials.

Will the recruitment plan propose to use any Penn media services (communications, marketing, etc.) for outreach via social media avenues (examples include: Facebook, Twitter, blogging, texting, etc.) or does the study team plan to directly use social media to recruit for the research?\*

NO

Subject compensation: Will subjects be financially compensated for their participation?

Yes

Summarize any financial compensation that will be offered to subjects, e.g. cash payments, gift card, reimbursement for travel. The amount of compensation may not constitute an undue inducement to participate in the research. A prorated system of financial compensation is required in most circumstances. Provide the schedule for compensation per study visit or session and total amount for entire participation.

Each subject will receive a \$100 gift card or online gift code as an incentive for completing the 6 hour study session. If provided a cashcard, we will work through the Greenphire clincard system (SOP attached to this submission). Information about the greenphire system will be provided during the consent process for the participant. Information, including social security number, will be collected from the participant at the intake phone call in order to set up an online account that the participant will be able to access. Participants will be reimbursed for travel and ensured a ride home by receiving either a septa token or up to \$30 in rideshare credits.

Suicidal Ideation and Behavior: Does this research qualify as a clinical investigation that will utilize a test article (ie- drug or biological) which may carry a potential for central nervous system (CNS) effect(s)?

YES

During the intake survey participants will be assessed for suicidal ideation and behavior using the Columbia-Suicide Severity Rating Scale. Participants who exhibit suicidal ideation or behavior will be withdrawn from the study and provided resources.

Central nervous system (CNS) effect: the ability of a test article to enter into and potentially interact with the central nervous system (brain and spinal cord).

YES

Clinical Investigation: Any experiment that involves a test article and one or more human subjects that either is subject to requirements for prior submission to the Food and Drug Adminstration (FDA) under section 505(i) or 520(g) of the Federal Food, Drug, and Cosmetic Act, or is not subject to the requirements for prior submission to the FDA under these sections of the act, but, the results of which are intended to be submitted later to, or held for inspection by, the FDA as part of an application for a research or marketing permit.

NO

**Procedures:** Describe study procedures. Include a table or flow chart, if necessary, showing the schedule of the procedures and interactions. It is important to distinguish between inventions that are experimental and carried out for research purposes versus those that are considered standard of care. In addition, routine procedures that are performed solely for research purposes should also be identified.

There will be 4 phases of the study:

1. Recruitment: We will use broad-based and cost-effective recruitment strategies including: a) advertisements in UPHS and CHOP employee weekly emails; and b) posting of flyers. Individuals, who are interested in the study, will be contacted and screened over the telephone.
2. Phone Screening: General information will be provided to the prospective subject. Study screening form (attached) will be administered, eligibility confirmed, and research staff will go over informed consent with participant. Participants will have the option to have the informed consent form emailed to them prior to the study visit. Columbia suicide severity rating scale will be administered. Inclusion criteria will be: (a) age 21-39 old, (b) Less than 4 drinking days and 12 drinks per week on average in the past 2 months, (c) have consumed either 4 (women) or 5 (men) or more standard drinks on a single occasion without problems (d) a valid photo ID (e) willing to take public transportation home, via septa or a rideshare credit. Exclusion criteria will be (a) desire alcohol treatment now or received it in the past 6 months, (b) alcohol dependence with withdrawal per DSM-V criteria (c) non-English-speaking, and (d) individuals who have a medical condition or who are taking medication which limits or prevents the consumption of alcohol. Interested and eligible participants will schedule their study visit.
3. Study Visit: On a predetermined study date, eligible subjects will come to the study site for a bar-lab session (timeline below), which will be conducted in the Center for Human Phenomic Science. Participants will be taken to a private room to review and sign the informed consent form. Before reviewing the consent, the research assistant will verify the participant is over 21 by checking their photo ID. After their age is confirmed and they are deemed eligible, the participant will review and sign the informed consent form. If the participant cannot produce a photo ID or their photo ID shows they are under 21 years old or over the age of 39, the CHPS appointment will be cancelled. Each study session will comprise of up to 4 participants, one per bed, and last about 5-6 hours. Prior to the test sessions they will be instructed to eat a small meal before fasting for 2 hours, abstain from caffeine for 8 hours and alcohol for 24 hours. Upon arrival, subjects will sign written informed consent. After which the subjects will undergo BrAC measurement, confirming a breath sample of 0 BrAC, using the BackTrack mobile device and complete a screening and medical history. At the CTRC participants will undergo a brief medical screening which will include measuring their blood pressure, heart rate, a urine pregnancy test for female participants. This screening will be performed by a CTRC nurse, who will be trained in the protocol.

**Intake Survey:** After which an intake survey will be administered by study staff, which includes a) Driving History and Experience Questionnaire DHEQ(Harrison & Fillmore, 2005), b) Drinking and Driving Questionnaire(McCarthy, Niculete, Treloar, Morris, & Bartholow, 2012), c) , this survey measures participants drinking habits during a single week, frequency of drinking, typical duration of drinking events, and number of months an individual has been drinking on a regular basis. Participants will then complete the Decision Making Survey, which has questions related to their Delayed discounting and measures of impulsivity (Senecal, Wang, Thompson, & Kable, 2012).

Dose Administration: Before dose administration a portion of participants will be instructed to wear the Bactrack skyn wearable device. All subjects will first be given a priming dose of alcohol containing vodka in fruit juice designed to raise the BrAC to 0.03-0.04 g/dL based on weight and gender (Watson et al., 1981). Subjective ratings of alcohol's effects and BrAC will be obtained after each dose. Each dose will be consumed within a standard 10-minute block to minimize inter-subject variability in the consumption rate. After each drink, participants will wait 20 minutes, and be instructed to rinse their mouth with a nonalcoholic mouthwash or water to ensure proper results. Breath alcohol content (BrAC) will be measured with BacTrack Pro commercial smartphone-paired breathalyzer (BACtrack Mobile Pro, n.d.) and recorded on a study smartphone using the BacTrack mobile app.

For participants in the control group, they will be blinded to the BrAC readings recorded on the BacTrack mobile app throughout the course of the study. For participants in the intervention group, they will be shown their BrAC readings on the BacTrack mobile app as they are measured.

This process will be repeated two times at minute 40 and minute 80. After each BrAC measurement has been obtained, we will also measure self-reported intoxication rating using: Self-Reported intoxication Survey, which includes: a) Perceived DriverFitness (Van Dyke & Fillmore, 2014) and b) Perceived intoxication and BAC estimation. (Harrison & Fillmore, 2005; Harrison et al., 2007) (survey attached).

After 150 minutes if participants BrAC does not measure .03 or below, participants will be tested at intervals of 20 minutes until their blood alcohol content has reached a level of .03 or below at which time they will be provided with transportation home. Midway through the study participants will receive a small meal provided by the CTRC.

